The use of Chaperone in Routine First Visit Examination of Women

Date: August 6, 2018.

1. Introduction

Guidelines for the presence of a chaperone, usually a female nurse, during intimate physical examination (eg, gynecological examination) vary according to country. In England, the General Medical Council recommends that all patients undergoing an intimate examination should be offered the possibility of an chaperone, irrespective of the gender of the patient or the gender of the physician (1, 2). In the United States, there is no national recommendation regarding the need for chaperones, and this recommendation is at the discretion of each state (3,4). Similarly, in Canada, the guidelines vary between provinces. For example, in Ontario there is the concept that both doctor and patient have the right to demand the presence of a third person during an intimate examination and, if necessary, insist that the examination be postponed if a third person is not present (5).

The use of chaperones depends, essentially, on the individual decision and preference of each doctor. In a study conducted in the United States, it was shown that male medical residents are more likely to use companions during a gynecological examination, but less likely to do so during breast examination or rectal examination. For female residents, the probability of using a chaperone was significantly lower. In addition, the use of chaperones during intimate exams performed in men was much lower than that seen in women (6).

In a similar study conducted in England, it was observed that 45% of general male clinicians never or rarely used chaperones in intimate examinations of women. Only 2% (3/178) of physicians used chaperones when examining men and only 8% of physicians did when examining women (7).

There are few studies, however, analyzing the patient's perception of whether or not a chaperone is needed. A study conducted in England attempted to evaluate patients' preference regarding this issue. Questionnaires on the subject were sent to men and women. A total of 190 men and 264 women answered these questionnaires. Of them, 15% were clearly opposed to the presence of companions, while 15% would like a chaperone to be present. The vast majority (59%) replied that they would feel uncomfortable if the chaperone was present without this being authorized by them. Most of the patients that did not want a chaperone considered uncomfortable to have to be exposed to a third person during the examination, which would reduce confidentiality of the consultation and also the trust between doctor and patient (8). A similar study conducted in Australia, also through mail-in questionnaires, showed that more women would be more comfortable with the presence of a chaperone if the examining physician was male compared to the situation in which the physician was a female (31% vs. 14%, P <0.01) (9).

Although the anorectal examination is part of the coloproctological routine, there is no published guideline regarding the need for the presence of a third person during this procedure. In addition, there is no publication so far evaluating the patients' perception of the need and adequacy of the presence of a chaperone during the proctological examination. What is seen in practice is that this decision of having a chaperone varies from doctor to doctor. In our Coloproctology Division, none of the physicians use to have a chaperone during the examination of female patients.

Considering the practical and legal implications of using a chaperone during the routine proctological examination, we propose a prospective study evaluating the perception of female patients regarding this issue.

2. Rationale

Although anorectal examination is part of the coloproctological routine, there is no guidance on the need for chaperone during the examination of female patients. Likewise, there is no study evaluating the patients' perception regarding the use or not of a chaperone during the proctological examination.

3. Objectives

3.1 General Objective:

To evaluate the degree of satisfaction of patients submitted to proctological examination with or without the presence of a chaperone.

3.2 Specific Objectives:

Correlate the degree of satisfaction of the patients with several clinical-demographic variables, including: age, marital status, diagnosis, comorbidities, symptomatology.

4. Hypotheses

Hypothesis 1: most patients will be satisfied without the presence of a chaperone during the anorectal examination.

Hypothesis 2: Most patients will be dissatisfied without the presence of a chaperone during the anorectal examination.

5. Materials and Methods

5.1 Study population

Adult women (18 years of age or older) who present for an initial consultation at our Coloproctology Division will be studied. These patients will be randomized into two groups:

- 1- Patients undergoing proctological examination with the presence of a chaperone.
- 2- Patients undergoing proctological examination without the presence of a chaperone.

The chaperone will always be a female, and may be a nurse or nursing assistant. Her participation will be communicated to the patient, who must agree to her presence during the proctological examination. After the consultation is completed, the patient will be informed that a study is being conducted and, if she agrees to participate, she should answer a specific questionnaire regarding the physical examination that was just performed. The purpose of the study will be explained, as well as the fact that participation is voluntary, not will change her clinical management, being guaranteed the secrecy and inviolability of the information obtained.

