5.2 Exclusion Criteria

Refusal to participate in the study. Patients already under follow-up within our Division will not be included (only first visits). In addition, patients who undergo diagnostic or therapeutic procedures during the appointment (which is rare in first visit), such as hemorrhoid elastic ligation, will not be included in the study.

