5.3. Primary Outcome Measure

The main outcome to be assessed will be patients' preference regarding the presence of a female chaperone during anorectal examination. It will also be assessed the degree of comfort (or embarrassment) according to the presence or not of a female chaperone during the proctological exam. This will be measured through a questionnaire compound of 6 questions (see Annexes 1 and 2). Each question will provide a isolated result (there will be no total score). The questions are the following:

1. How did you feel during the exam?
Patients will register their answer in a scale from zero (completely embarrassed) to 10 (completely comfortable)
2. What did you think of (not) having a person besides the doctor during the exam?
Patients will have 3 possible answers: bad, indifferent, good.
3. Would you rather have taken the exam in the (without) presence of another person (woman)?
There are 3 possible answers: yes, no, indifferent.
4. Do you think the (absence) presence of another person made the examination:

There are 3 possible answers: better, worse, did not change it.

5. Did you feel more (less) protected with (without) the presence of another person?

There are 3 possible answers: yes, no, indifferent.

6. In the event of a reexamination, would you want another person's presence again?

There are 3 possible answers: yes, no, indifferent.

Or: Would you again like the doctor to examine you without another person's presence?

There are 3 possible answers: yes, no, indifferent.

6. Ethical aspects

This research project follows the Normative Resolution 01/97 of the Commission for Research and Ethics in Health, as part of the Research Group and Post-graduation Program/ HCPA. There will be no change in medical investigation and management whether or not the patient decides to participate in the study. The researchers guarantee to preserve the privacy of patients whose data will be collected, to use this information solely and exclusively for the execution of this project and to publish the information obtained only anonymously.

7. Budget and sources of funding

There will be no additional cost to the HCPA with the completion of the study. The computer equipment and software required for data recording and its subsequent analysis are already available at our Division, and there is no need for new acquisitions or financing.

8. Sample size

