The sample size was calculated based on a study conducted by Teague et al. (9), which showed that a larger number of women is more comfortable with the presence of a chaperone if the examining physician was a man, compared to the situation in which the examination was conducted by a female physician (31% vs. 14%, $P < 0.01$) (9). Using these differences, with 90% power and 0.05 error was estimated through the SPSS program, it would be required a total of 94 patients in each study group (with or without companion). Considering the volume of first visits attended in our Division of Coloproctology, it is estimated that the data collection will be completed in approximately two years.

9. Statistical Analysis Plan

Categorical variables will be described by absolute and relative frequency (percentage). The quantitative variables with symmetrical distribution will be described by the mean and standard deviation.

Quantitative variables with asymmetric distribution will be described by median and interquartile range (percentiles 25 and 75). Chi-square or Chi-square tests with Yates correction will be used to compare the categorical variables. Quantitative variables with symmetrical distribution will be compared by the Student t test for independent samples. Quantitative variables with asymmetric distribution will be compared by the Mann-Whitney test. A level of statistical significance of 5% shall be considered in all tests used.

10. Cronogram of Activities

Date	Activities
January and February 2018	Elaboration, submission and approval of the research project
July 2018 to July 2020	Data collect
August to September 2020	Statistical analysis
October 2020	Bibliographic review and elaboration of the scientific article

12. References

- 1- The Royal College of Obstetricians and Gynaecologists. Gynaecological examinations, guidelines for specialist practice. London: RCOG, 2002.
- 2- Intimate Examinations. London, UK, General Medical Council. December 2001.
- 3- Gawande A: Naked. *N Engl J Med* 2005, 353(7):645-648.
- 5- College of Physicians and Surgeons of Ontario: Avoid complaints of sexual abuse (policy document) [<http://www.cpso.on.ca/Policies/avoid.htm>].

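### The plan does not say in which group a woman who declines the chaperone is analysed; dropping or switching her would select an arm on the primary outcome

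*Combined protocol and SAP*

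**What the plan says.** Section 5.1 states: "These patients will be randomized into two groups". It words each group by the examination that takes place, for example "Patients undergoing proctological examination with the presence of a chaperone". It then says of the chaperone: "Her participation will be communicated to the patient, who must agree to her presence during the proctological examination". The study itself is disclosed later: "After the consultation is completed, the patient will be informed that a study is being conducted and, if she agrees to participate", she answers the questionnaire.

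The only refusal among the exclusions in Section 5.2 is "Refusal to participate in the study". The main outcome in Section 5.3 is "preference regarding the presence of a female chaperone during anorectal examination".

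Section 8 counts the groups in the same way as Section 5.1: "it would be required a total of 94 patients in each study group (with or without companion". Section 9 gives the test, "Chi-square or Chi-square tests with Yates correction will be used to compare the categorical variables", and a 5% level. It names no analysis population and has no rule for a woman whose examination differs from her allocation, or for missing questionnaires.

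**The concern.** Only a woman allocated to a chaperone has one to accept or decline, so the agreement step can act on one arm alone. Declining is itself an expression of the primary outcome. A woman who declines does not fit the description of group 1, and the plan neither keeps her there nor says which questionnaire she receives.

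If she is dropped, group 1 loses women opposed to a chaperone while group 2 keeps them. If she is examined alone and counted in group 2, group 1 loses them and group 2 gains them. Either way the groups compared are no longer those that randomisation made, and the difference leans towards the chaperone even if allocation has no effect.

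The between-group comparison is what is exposed. The hypotheses in Section 4 concern women examined without a chaperone, so they are touched only if decliners are switched into that group.

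**Working it through.** **Order of events.** The text does not state the order of allocation and agreement. Two features support agreement after allocation: Section 5.1 describes randomisation first, and women hear of the study only after the consultation. That agreement concerns one arm follows from there being no chaperone in the other. This is an inference, though a strong one.

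**The plan's own figure.** The illustration needs a group size, so the 94 in Section 8 was checked. With 31% vs 14%, the mean proportion is 0.225 and

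n = [1.96·√(2·0.225·0.775) + z·√(0.31·0.69 + 0.14·0.86)]² / 0.17².

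- 90% power (z = 1.2816): (1.157 + 0.741)² / 0.0289 = 124.7, so 125 per group.
- 80% power (z = 0.8416): (1.157 + 0.487)² / 0.0289 = 93.5, so 94 per group.

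The stated 94 thus matches 80% power, not the stated 90%. That is a separate matter. Here 94 serves only as the number analysed per group.

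**Inputs of the illustration**

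- Share opposed to a chaperone, *o*: 15%, from the mixed-sex questionnaire survey cited in Section 1. It is not a planning value, so 5% is shown as well.
- Share of opposed women who decline, *r*: 25%, assumed. This is 0.15 × 0.25 = 3.75% of women offered a chaperone, or 1.25% when *o* = 5%.
- Only opposed women decline, and allocation has no true effect: both assumed.
- The answer is a binary item (opposed or not) constructed for this check; 94 women are analysed per group.

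**Expected shares opposed**

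- Group 1 without its decliners: *o*(1 − *r*) / (1 − *or*). For 15%: 0.1125 / 0.9625 = 11.7%. For 5%: 0.0375 / 0.9875 = 3.8%.
- Group 2 if decliners are lost: *o*.
- Group 2 if decliners are switched into it: *o*(1 + *r*) / (1 + *or*). For 15%: 0.1875 / 1.0375 = 18.1%. For 5%: 0.0625 / 1.0125 = 6.2%.

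**False-positive rate.** Sum the product of the two binomial probabilities over all counts (a, b) from 0 to 94 for which 188·(|a − b| − k)² / [s(188 − s)] exceeds 3.84, where s = a + b, k = 0 for Pearson and k = 1 for Yates (numerator set to zero when a = b).

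| Opposed | Decliners | Group 1 vs group 2 | Pearson | Yates |
|---|---|---|---|---|
| 15% | none decline | 15.0% vs 15.0% | 5.0% | 3.2% |
| 15% | lost | 11.7% vs 15.0% | 10.2% | 6.9% |
| 15% | switched | 11.7% vs 18.1% | 23.2% | 17.9% |
| 5% | lost | 3.8% vs 5.0% | 5.8% | 2.5% |
| 5% | switched | 3.8% vs 6.2% | 10.0% | 5.2% |

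With 15% opposed and decliners lost, 9.7 of the 10.2 Pearson points favour the chaperone. With 10% opposed and decliners lost, the rates are 8.7% and 4.6%.

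**Sensitivity to the assumptions**

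- *Decline rate, 15% opposed.* If a tenth of opposed women decline, the rates are 5.7% / 3.7% (lost) and 7.7% / 5.2% (switched), Pearson / Yates. If half decline, they are 31.8% / 23.7% and 72.0% / 65.0%.
- *Coding.* A three-category test (assumed 15% opposed, 15% wanting a chaperone, 70% indifferent) with a quarter of opposed women declining gives about 8% lost and 18% switched, by simulation. Testing the share who want a chaperone (15% assumed) barely moves: 5.6% lost and 7.1% switched (Pearson), even if half of opposed women decline.
- *Analysis by allocation.* If every decliner gives her own answers, the rate is 5.0% (Pearson) or 3.2% (Yates).

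**The case against.** The strongest case on the other side is that this is a gap in the text and not a stated error. Four parts of it stand.

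- The order of agreement and allocation is inferred. Asking every woman before allocation is not excluded, though it fits poorly with disclosing the study only after the visit.
- No decline rate is given. Few women may decline, and the bias is nil if nobody does.
- The tested variable is constructed. Section 5.3 reports six separate items and defines no opposed/not-opposed answer.
- Under the Yates correction, which Section 9 allows, inflation is small or absent in several moderate scenarios.

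A reader might infer that the plan prescribes analysis by the examination received, or that it discards decliners. The documents do not support that: the wording of the groups leaves the question open and does not rule out analysis as randomised. A reader might also infer that the Section 4 hypotheses are undermined. They are unaffected if decliners are lost. If they are switched at 7.5% of those offered and all are satisfied, a true 50% satisfied becomes (0.50 + 0.075) / 1.075 = 53.5%.

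One defence fails. The study refusal in Section 5.2 is asked of both arms after the examination, so it does not settle how chaperone decliners are analysed. Stretching it to cover them would remove women from one arm only, which is the bias at issue.

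**Conclusion.** The point holds as a gap that should be closed, with medium confidence. As worded, the plan leaves a woman who declines without a group, and two obvious ways of handling her (dropping or switching) would select at least one arm on the primary outcome, in a predictable direction.

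The size cannot be established from the documents. In the illustrations with a quarter of opposed women declining, the false-positive rate runs from no inflation (5% opposed, decliners lost, Yates 2.5%) to 23% (15% opposed, switched, Pearson). These figures rest on an assumed decline share, on only opposed women declining, and on a constructed binary answer. They show what could happen and do not predict this trial's error rate.

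**What to change.** 1. Keep an anonymous count of women allocated to each arm, and report chaperone declines and study refusals by arm. Limiting this to counts respects the fact that consent comes after the visit.
2. Offer decliners the same post-visit questionnaire, in the version that fits the examination they had.
3. Make the primary between-group comparison of preference (questions 3 and 6) by allocated group, using decliners' own answers recoded to prefers chaperone / indifferent / prefers none. Recoding is needed because a yes to either question means opposite things in the two versions. Add best- and worst-case bounds for women without answers: 4 or 7 such women out of 94 widen that group's share by 4/94 = 4.3 or 7/94 = 7.4 percentage points.
4. Report the comfort score (question 1) by allocated group. Report questions 2, 4 and 5, whose wording depends on the version, descriptively by examination undergone, labelled as non-randomised. Show any as-examined comparison of preference as a sensitivity analysis only.

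Do not count declining itself as opposition, except as one bound. If 5% of indifferent women (70% assumed) also declined and were counted as opposed, group 1 would show 0.15 + 0.05 × 0.70 = 18.5% against 15%, and the false-positive rate would be 9.7% (Pearson) or 7.0% (Yates).

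The cost is a tally sheet, a few lines in Section 9 and possibly ethics approval for the counts. Decliners will dilute the contrast between examined conditions somewhat. Bias remains if decliners also refuse the questionnaire: with 15% opposed and half of them declining, the rate by allocation is 10% / 7% (Pearson / Yates) if half of the decliners refuse it, and 32% / 24% if all do. The bounds would make that visible. The woman's right to decline is unchanged.

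### Women enter the study only after their arm has been delivered and seen, and no register or analysis by allocated arm is described, so randomisation cannot be relied on to protect the comparison

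*Combined protocol and SAP*

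**What the plan says.** Section 5.1 defines the population broadly: "Adult women (18 years of age or older) who present for an initial consultation at our Coloproctology Division will be studied". On allocation it says only "These patients will be randomized into two groups". It does not say how the sequence is generated, who holds it or whether it is concealed.

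The order of events is clear. The examination takes place with or without the chaperone, and study entry follows: "After the consultation is completed, the patient will be informed that a study is being conducted and, if she agrees to participate, she should answer". What she is then given is "a specific questionnaire regarding the physical examination that was just performed".

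The chaperone arm has a further step that the other arm lacks: "Her participation will be communicated to the patient, who must agree to her presence during the proctological examination". The plan does not say how a woman who declines is counted.

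Section 5.2 lists as an exclusion "Refusal to participate in the study". It also excludes women who have a procedure at the appointment, which it describes as rare. Both can arise after allocation.

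Section 9 lists unadjusted two-group tests at the 5% level. It names no analysis set and does not say whether women are compared by the arm allocated or the arm received.

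**The concern.** Randomisation makes two groups comparable at the moment of allocation. The benefit lasts only if the women analysed are those allocated, or if losses are unrelated to the arm and the outcome. Here the group analysed is formed after the arm has been experienced, in a trial where the arm cannot be masked. The outcomes are the woman's own preference and comfort, so the experience that might lead her to stay out is close to what is being measured.

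The text shows two routes by which entry can depend on the arm. A woman may refuse the questionnaire after an examination she disliked. A woman allocated to a chaperone may decline the chaperone. A third route is possible but not stated: uneven invitation by staff who know the arm.

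With no list of everyone allocated, losses by any route could not be counted per arm. A resulting bias could be neither detected nor bounded after data collection.

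**Working it through.** **Plan's own figure.** Section 8 gives 94 per group for 31% vs 14%. The pooled two-sided 5% formula gives [1.96·√(2·0.225·0.775) + 0.8416·√(0.31·0.69 + 0.14·0.86)]² / 0.17² = 93.5, so 94, at 80% power. With 1.2816 in place of 0.8416, for the stated 90% power, it gives 124.7, so 125. That mismatch is a separate matter. Below, 94 per arm is used as stated.

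**Inputs.** From the documents: 94 per arm, a 5% level and a chi-square test (sections 8 and 9). The true share wanting a chaperone, *p*, is set equal in both arms, so there is no real difference. The values tried are 31%, 14% and their midpoint 22.5%. Section 8's rates come from a survey split by the physician's sex, so they serve only as plausible values. Every loss fraction is an assumption, because the documents give none. Recruitment is taken to continue until 94 women per arm have answered.

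**Model 1: loss tied directly to preference.** A fraction *s* of the women wanting a chaperone is lost from one arm only. The share observed in that arm is q = p(1 − s)/(1 − ps). For p = 0.31 and s = 0.25, q = 0.2325/0.9225 = 0.252, a bias of 5.8 points. The false-positive rate is the probability that the two-sided 5% Pearson chi-square without correction rejects, found by full binomial enumeration.

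| Loss *s* | p = 31%: bias, rate | p = 22.5%: bias, rate | p = 14%: bias, rate |
|---|---|---|---|
| 0 | 0, 5.0% | 0, 5.0% | 0, 5.0% |
| 10% | 2.2 points, 6.2% | 1.8 points, 6.0% | 1.2 points, 5.7% |
| 25% | 5.8 points, 14.1% | 4.6 points, 12.3% | 3.1 points, 9.9% |
| 50% | 12.7 points, 52.4% | 9.8 points, 42.7% | 6.5 points, 30.3% |

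Section 9 also allows the Yates correction. With it, the 25% row becomes 11.0%, 9.2% and 6.5%, against 3.1% to 3.5% with no loss.

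**Model 2: loss tied to an imperfect sign.** Suppose half of the women wanting a chaperone, and 20% of the others, show some visible sign such as discomfort, and a fraction *s* of those showing it is lost from one arm. Then q = p(1 − 0.5s)/[p(1 − 0.5s) + (1 − p)(1 − 0.2s)]. For p = 0.31 and s = 0.5, q = 0.2325/0.8535 = 0.272. Across the three values of *p*:

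- s = 25%: bias 1.0 to 1.7 points, false-positive rate 5.4% to 5.7%.
- s = 50%: bias 2.1 to 3.8 points, false-positive rate 7.0% to 8.7%.

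**Model 3: the agreement step.** The Introduction cites an English survey of men and women in which 15% were clearly opposed to a chaperone. If all such women left the chaperone arm only, and none of them belonged to the share wanting one, then q = p/0.85. The observed share rises from 14% to 16.5%, or from 31% to 36.5%: a spurious difference of 2.5 to 5.5 points. The false-positive rate is 7.5% to 12.7% by the same enumeration.

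**Direction.** If women wanting a chaperone refused more often after an examination without one, and women opposed declined in the other arm, both losses would push the difference the same way.

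**The case against.** The strongest reply is that section 5.1 can be read as already inviting everyone. It says that women at a first visit will be studied and randomised, and that the patient will be told of the study. No step lets anyone pass a woman over. Four stronger readings are tempting, and the documents do not support them.

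- **Staff select whom to invite.** A reader might infer this from the open arm and from the Introduction's remark that "In our Coloproctology Division, none of the physicians use to have a chaperone during the examination of female patients". That sentence reports habit. It does not show a wish for a particular result or any screening of patients. Selective invitation, or an allocation overridden for want of a nurse, would depart from section 5.1. Uneven invitation is a possibility that nothing in the plan checks, and no more.
- **No concealed list or register exists.** The plan is short and silent on both. Silence does not prove absence.
- **The comparison is biased.** If entry is equal in both arms and unrelated to the outcome, there is no bias.
- **The false-positive rate is about 50%.** That needs half of the women wanting a chaperone to vanish from one arm only. If staff selection were the cause, staff would have to know a preference first recorded in the questionnaire.

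These replies limit the claim without removing it. Refusal after the examination, and the agreement required in one arm only, are in the text. Both operate when the plan is followed exactly as written. This is therefore more than an undescribed randomisation detail.

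**Conclusion.** The concern holds in limited form. The plan's order of events lets entry depend on a known arm, and the documents describe nothing that would reveal or contain this. Randomisation cannot be relied on to protect the comparison of preference and comfort, though it has not been shown to fail.

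The size is unknown, because it depends on rates of refusal, of declining the chaperone and of invitation that the documents do not give. With no true difference, 94 per arm, an uncorrected chi-square and loss in one arm only, plausible false-positive rates run from about 5–9% for weak selection to 10–14% when a quarter of the women wanting a chaperone are lost. The 30–52% range is an extreme case. The improvement is cheap and worth making, since a register cannot be rebuilt once data collection is over.

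**What to change.** **Section 5.1.** Enter every eligible first-visit woman in a numbered register before her arm is revealed. Reveal the arm from a concealed, computer-generated list. Invite every registered woman after the visit. Record in the register the arm drawn, the arm delivered, whether she declined the chaperone, whether she was invited and whether she refused. A procedure at the appointment should be recorded there too.

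**Section 9.** Make the primary comparison by arm drawn. Report the counts at each step per arm. Add a sensitivity analysis for registered women without answers, for example bounds that count them all as wanting a chaperone and then all as not wanting one.

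Concealment alone does not cure selection that happens after allocation. The register, the counts per arm and the analysis by arm drawn are the parts that matter. Analysis by arm drawn cannot recover missing answers, which is why the sensitivity analysis is needed.

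The timing of disclosure can stay as it is; consent timing is for the ethics committee. The cost is one amendment, one list and a little clerical work at each clinic. No additional visits are needed, and the target of 94 answers per arm does not change.
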